3.9 Screen Failures

A screen failure subject is one from whom informed consent is obtained and is documented in writing (ie, subject signs an ICF), but who is not randomized or assigned trial treatment.

Screen failures may be rescreened at any time if the exclusion characteristic has changed. Subjects who sign an ICF but who are not started on treatment are permitted to be rescreened. In the event that the subject is rescreened for trial participation, and the rescreening is not completed within the original screening window, a new ICF must be signed.

3.10 Definition of Completed Subjects

The treatment period is defined as the time period during which subjects are evaluated for primary and/or secondary objectives of the trial irrespective of whether or not the subject actually consumed all doses of the IMP. Subjects who are evaluated at the last scheduled visit during the treatment period will be defined as trial completers. For purposes of this trial, subjects who complete Day 21 visit will be defined as trial completers.

3.11 Definition of Subjects Lost to Follow-up

Subjects who cannot be contacted on or before Day 21 visit during the treatment period, who do not have a known reason for discontinuation (eg, withdrew consent or AE), and for whom a survival status at the end of the trial cannot be determined will be classified as “lost to follow-up” as the reason for discontinuation. Survival status can be determined from a variety of sources, either by obtaining acceptable documentation for death (ie, death certificate, medical records, public records, statement by a family member or primary care physician) or acceptable documentation for life (ie, direct contact with the subject, medical records, successful telephone contact with the subject, statement by a family member or primary care physician, or public records).

The site will make 3 documented attempts to contact the subject by telephone and in the event the site is unable to reach the subject by telephone, the site will attempt to contact the subject via certified mail or an alternative similar method, where appropriate, before assigning a “lost to follow-up” status.

3.12 Subject Compliance

Responsible trial personnel will dispense the IMP. Accountability and compliance verification should be documented in the subject’s trial records. Subjects must be counseled on the importance of taking the IMP as directed at all trial visits. If poor compliance continues (eg, multiple missed doses resulting in less than 80% overall compliance at any point in the trial), discontinuation of the subject from the trial should be considered. The medical monitor should be contacted if the investigator is uncertain whether a subject's lack of compliance merits discontinuation from the trial.

3.13 Protocol Deviations

In the event of a significant deviation from the protocol due to an emergency, accident, or mistake (eg, violation of informed consent process, IMP dispensing or subject dosing error, treatment assignment error, subject enrolled in violation of eligibility criteria or concomitant medication criteria), the investigator or designee will contact the medical monitor at the earliest possible time by telephone. The investigator and medical monitor will come as quickly as possible to a joint decision regarding the subject’s continuation in the trial. This decision will be documented by the investigator and the medical monitor, and reviewed by the site monitor.

4 Restrictions

4.1 Prohibited Medications

All subjects must agree to discontinue all prohibited medications during the screening period in order to meet the protocol-specified washout periods. Table 4.1-1 provides the required duration of washout for selected prohibited medications. All other prohibited medications must be discontinued at least 24 hours before the first dose of IMP. Subjects who are receiving prohibited medications that would require a washout of more than 14 days (eg, current use of depot or long-acting injectable antipsychotics) are excluded from the trial. However, subjects whose last injection of antipsychotic occurred at least one full cycle (based on the prescribing label) before the initial screening visit are eligible to enter the 14-day screening period if at least one full cycle plus 1/2 cycle (length of 1 cycle based on the prescribing label) will have elapsed before randomization. Subjects with serum concentrations of lithium ≥ 0.6 mmol/L, valproate ≥ 50 $\mu\text{g/mL}$, or carbamazepine ≥ 4 $\mu\text{g/mL}$ at screening may repeat a clinical laboratory test for these parameters prior to randomization. The results of the additional test will be reviewed and confirmed before the subject can be randomized into the trial. Other therapies restricted or prohibited prior to enrollment and during the trial are presented in [Section 4.2](#).

Medication	Required Washout Prior to Dosing
Antipsychotics Oral (or IR IM) aripiprazole Other oral (or IR IM) antipsychotics Depot or long-acting injectable antipsychotics	14 days 7 days One full cycle plus 1/2 cycle ^a (length of 1 cycle based on the prescribing label)
Antidepressants Fluoxetine or Symbyax MAOIs Citalopram and escitalopram Venlafaxine and desvenlafaxine All other antidepressants	28 days ^a 14 days 8 days 3 days 14 days
Mood stabilizers (ie, lithium and/or anticonvulsants)	7 days
Varenicline	5 days
Benzodiazepines	Refer to Section 4.1.1 for details on benzodiazepine use during the trial
CYP2D6 inhibitors and CYP3A4 inhibitors and inducers	14 days

IR IM = immediate-release intramuscular; MAOIs = monoamine oxidase inhibitors.

^aSubjects must satisfy the washout restriction within the 14-day screening period. Therefore, subjects currently receiving depot or long-acting injectable antipsychotics, fluoxetine, or Symbyax at screening are excluded from the trial. However, if these medications were recently discontinued prior to the initial screening visit for reasons unrelated to this trial and the required washout will be met within 14 days of the initial screening visit, the subject may be screened for the trial.

Table 4.1-2 lists all medications prohibited during the trial, including exceptions, where appropriate.

Table 4.1-2 List of Medications Prohibited During the Trial	
1.	All psychotropic agents including, but not limited to, the following: a) Antipsychotics, including depot or long-acting injectable formulations b) Anticonvulsants c) Antidepressants (including MAOIs) d) Mood stabilizers (ie, lithium and/or anticonvulsants) e) Benzodiazepines, except specific benzodiazepines when used as rescue therapy ^a f) Prescription stimulants (including appetite suppressants and treatments for ADHD or narcolepsy) g) Opioid analgesics, unless permission is obtained from the medical monitor. Permission for opioid use may be considered for a documented and clinically appropriate indication (eg, episodic pain condition, tooth extraction) if prescribed at a medically appropriate dose and frequency). h) Nutritional supplements and non-prescription herbal preparations with CNS effects (eg, St. John's Wort, omega-3 fatty acids, kava extracts, gamma-aminobutyric acid supplements, etc)
2.	Hypnotics, including ramelteon and other non-benzodiazepine sleep aids, except for specific medications when used to manage treatment-emergent AEs related to insomnia ^b
3.	Antihistamines (except for loratadine and cetirizine)
4.	Varenicline
5.	Vitamins, other nutritional supplements, and non-prescription herbal preparations, unless approved in advance by the medical monitor
6.	Investigational agents.
7.	CYP2D6 inhibitors or CYP3A4 inhibitors and inducers. Selected CYP2D6 inhibitors are: celecoxib, hydroxyzine, chloroquine, methadone, chlorpheniramine, moclobemide, clemastine, clomipramine, pyrilamine, diphenhydramine, quinidine, terbinafine, halofantrine, tripeleminamine. Selected CYP3A4 inhibitors are: amiodarone, fluvoxamine, amprenavir, indinavir, aprepitant, itraconazole, chloramphenicol, ketoconazole, cimetidine, nefazodone, clarithromycin, nelfinavir, clotrimazole (if used orally), quinupristin/dalfopristin, delavirdine, ritonavir, diltiazem, saquinavir, erythromycin, troleandomycin, fluconazole, verapamil. Selected CYP3A4 inducers are: carbamazepine, oxcarbazepine, phenytoin, dexamethasone, primidone, efavirenz, rifampin, nevirapine, St. John's Wort, phenobarbital, troglitazone. The medical monitor should be consulted for any questions regarding the potential for pharmacokinetic interactions with concomitant medications used by subjects during the trial.)

^aRefer to [Section 4.1.1](#) for details on benzodiazepine use during the trial.

^bNon-benzodiazepine sleep aids (ie, zolpidem, zaleplon, zopiclone, and eszopiclone only) are permitted for the treatment of insomnia, but not on the same day as administration of a benzodiazepine, regardless of indication. For the non-benzodiazepine sleep aids, sites should only utilize one of the listed medications that are approved for this indication in their respective countries and the country-specific prescribing information is to be used to determine the maximum allowable daily dose for the treatment of insomnia. Non-benzodiazepine sleep aids must not be administered within 8 hours prior to scheduled efficacy and safety assessments, including EPS scales. Investigators are encouraged to

delay scale administration until 8 hours have elapsed, if at all possible. However, if delaying administration of efficacy and safety scales is not feasible, the scales should still be administered and the use of the sleep aid documented, including a notation of the drug name, dose, and time of administration on the eSource.

4.1.1 Use of Benzodiazepines During the Trial

The use of IM benzodiazepines and continual use of oral benzodiazepines is prohibited during this trial. However, limited use of oral lorazepam as a rescue medication for the short-term management of treatment-emergent AEs (TEAEs) of anxiety, agitation, and insomnia will be allowed both during the washout period between the screening and baseline assessments, and during the treatment phase. Lorazepam equivalents are prohibited unless explicitly authorized by the medical monitor. During the washout period, the prior use of other benzodiazepines must be discontinued in favor of oral lorazepam. During the treatment phase, use of oral lorazepam must follow the daily dose schedule listed in Table 4.1.1-1 for Days 1 through 14. All benzodiazepine use, including lorazepam, is prohibited after Day 14.

In countries where lorazepam is not commercially available, the use of oral oxazepam, alprazolam, diazepam, or clonazepam is only acceptable with prior authorization from the medical monitor. The following guide should be used to determine approximate lorazepam equivalents: 1 mg lorazepam = 15 mg oxazepam = 0.5 mg alprazolam = 5 mg diazepam = 0.5 mg clonazepam. The prescribed benzodiazepine should be discontinued as soon as the AE for which it was initiated subsides, as per the investigator's discretion to avoid any withdrawal effects.

Benzodiazepines must not be administered within 8 hours prior to any scheduled efficacy or safety scale assessments. Investigators are encouraged to delay scale administration until a full 8 hours have elapsed since the last benzodiazepine dose, if at all possible, including at screening and baseline assessments. However, if delaying administration of efficacy and safety scales is not feasible, the scales should still be administered and the use of benzodiazepine documented, including a notation of the drug name, dose, and time of administration on the eSource.

Table 4.1.1-1 Oral Benzodiazepine Rescue Therapy During the Trial				
Oral Benzodiazepine	Maximum Allowable Dose (mg/day)			
	Days 1-4	Days 5-7	Days 8-10	Days 11-14
Lorazepam ^a	6	4	2	1

^aIn countries or institutions where lorazepam is not commercially available, use of oral lorazepam equivalents, as described in [Section 4.1.1](#) and dosed based on the schedule in Table 4.1.1-1 is

acceptable only with prior authorization from the medical monitor. All benzodiazepine use, including lorazepam, is prohibited after Day 14.

4.2 Other Restrictions

The subject's best medical interests should guide the investigator in the management of conditions that are pre-existing or that develop during the trial (intercurrent illness or AEs). The investigator should examine the acceptability of all concomitant medications not explicitly prohibited. In order to ensure that appropriate concomitant therapy is administered, it is essential that subjects be instructed not to take any medications (either self-administered non-prescription drugs or prescription therapy prescribed by another physician) without prior consultation with the investigator. In particular, the investigator should caution the subject about concomitant use of the following during the trial:

- Non-steroidal anti-inflammatory drugs, aspirin, or other drugs that interfere with coagulation since the combined use of psychotropic drugs that interfere with serotonin reuptake and these agents has been associated with an increased risk of upper gastrointestinal bleeding.¹⁹
- Triptans (eg, sumatriptan, naratriptan, almotriptan, frovatriptan, rizatriptan, eletriptan, and zolmitriptan), linezolid, and methylene blue since there have been rare post-marketing reports of serotonin syndrome or serotonin syndrome-like reactions (eg, mental status changes, hyperreflexia, autonomic effects, lack of coordination, and diarrhea) following the concomitant use of SSRIs or serotonin-norepinephrine reuptake inhibitors and these drugs.

Anticholinergics are permitted for the treatment of EPS up to a maximum of 4 mg/day benztropine or its equivalent and propranolol is permitted for akathisia or tremor up to a maximum of 20 mg 3 times daily (total of 60 mg/day). Sites should only utilize medications that are approved for these indications in their respective countries.

All trial personnel should be familiar with the content of the IB for brexpiprazole in order to manage the subject's condition adequately and select appropriate concomitant medications, if needed.

5 Reporting of Adverse Events

5.1 Definitions

An AE is defined as any untoward medical occurrence in a patient or clinical trial subject administered a medicinal product and which does not necessarily have a causal relationship with this treatment. AEs would not include information recorded as medical

history at screening for preplanned procedures for which the underlying condition was known and no worsening occurred. An adverse reaction is any untoward and unintended response to an IMP related to any dose administered.

A suspected adverse reaction is any AE for which there is a reasonable possibility that the IMP caused the AE. For the purpose of IND safety reporting, "reasonable possibility" means there is evidence to suggest a causal relationship between the IMP and the AE. Suspected adverse reaction implies a lesser degree of certainty about causality.

An SAE includes any event that results in any of the following outcomes:

- Death
- Life-threatening; ie, the subject was, in the opinion of the investigator, at immediate risk of death from the event as it occurred. It does not include an event that, had it occurred in a more severe form, might have caused death.
- Persistent or significant incapacity/disability or substantial disruption of the ability to conduct normal life functions.
- Requires inpatient hospitalization or prolongs hospitalization.
 - Hospitalization itself should not be reported as an SAE; whenever possible the reason for the hospitalization should be reported.
 - Hospitalizations or prolonged hospitalizations for social admissions (ie, those required for reasons of convenience or other non-medical need) are not considered SAEs.
- Congenital anomaly/birth defect.
- Other medically significant events that, based upon appropriate medical judgment, may jeopardize the subject and may require medical or surgical intervention to prevent one of the outcomes listed above; eg, allergic bronchospasm requiring intensive treatment in an emergency room or home, blood dyscrasias or convulsions that do not result in hospitalization, or the development of drug dependency or drug abuse.

Nonserious adverse events are all AEs that do not meet the criteria for a "serious" AE.

Immediately Reportable Event (IRE):

- Any SAE.
- Any AE related to occupational exposure.
- Potential serious hepatotoxicity (see [Section 5.4](#)).
- Pregnancies are also defined as IREs. Although normal pregnancy is not an AE, it will mandate IMP discontinuation and must be reported on the clinical trial pregnancy and breastfeeding form, or other designated form, to the sponsor.

Pregnancy will only be documented on the AE ePlatform if there is an abnormality or complication.

Clinical Laboratory Test Value Changes: It is the investigator's responsibility to review the results of all laboratory tests as they become available. This review will be documented by the investigator's dated signature on the laboratory report. For each abnormal laboratory test result, the investigator needs to ascertain if this is an abnormal (ie, clinically significant) change from baseline for that individual subject. This determination, however, does not necessarily need to be made the first time an abnormal value is observed. The investigator may repeat the laboratory test or request additional tests to verify the results of the original laboratory tests. If this laboratory value is considered medically relevant by the investigator (subject is symptomatic, requiring corrective treatment or further evaluation), or if the laboratory value leads to discontinuation, and/or fulfills a seriousness criterion, this is considered an AE.

Severity: Adverse events will be graded on a 3-point scale and reported as indicated on the ePlatform. The intensity of an adverse experience is defined as follows:

- 1 = Mild:** Discomfort noticed, but no disruption to daily activity.
- 2 = Moderate:** Discomfort sufficient to reduce or affect normal daily activity.
- 3 = Severe:** Inability to work or perform normal daily activity.

IMP Causality: Assessment of causal relationship of an AE to the use of the IMP is defined as follows:

- Related:** There is a reasonable possibility of a temporal and causal relationship between the IMP and the AE.
- Not Related:** There is no temporal or causal relationship between the IMP and the AE.

5.2 Eliciting and Reporting Adverse Events

The investigator will periodically assess subjects for the occurrence of AEs. To avoid bias in eliciting AEs, subjects should be asked the non-leading question: "How have you felt since your last visit?" All AEs (serious and nonserious) reported by the subject must be recorded within the eSource platform provided by the sponsor. All AE collection is to begin after a subject has signed the ICF.

Use medical terminology in AE reporting. Adverse events should be reported as a single unifying diagnosis whenever possible or, in the absence of a unifying diagnosis, as individual signs or symptoms. Exacerbation or disease progression should be reported as an AE only if there are unusual or severe clinical features that were not present, or experienced earlier, or not expected based on the course of the condition.

A reported AE that undergoes a change in severity, seriousness, or toxicity should be reported as a new AE on the ePlatform.

In addition, the sponsor must be notified immediately by telephone, fax, or e-mail of any IREs according to the procedure outlined below, in [Section 5.3](#). Special attention should be paid to recording hospitalization and concomitant medications.

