3.1 Type/Design of Trial

This will be a 3-week, multicenter, randomized, double-blind, placebo-controlled trial of brexpiprazole in subjects diagnosed with bipolar I disorder (current manic episode with or without mixed features) according to the *Diagnostic and Statistical Manual of Mental Disorders, Fifth Edition* (DSM-5; updated terminology replaces “mixed episodes” with the descriptor of “mixed features”). The total duration of the trial is up to 8 weeks, including screening, double-blind treatment, and follow-up. See Figure 3.1-1 for a schematic of the trial design.

The trial will be organized as follows:

Screening Phase: The screening period will begin after written informed consent has been obtained and will take place between Day -14 and Day -1 prior to randomization. Hospitalization will begin with the signing of the informed consent form (ICF) for subjects who are not already hospitalized at the time of the initial screening visit. The purpose of the screening period is to assess eligibility criteria and to washout prohibited concomitant medication. Subjects will be between 18 and 65 years of age, inclusive, at the time of screening, will have a diagnosis of bipolar I disorder, and will be experiencing a manic episode with or without mixed features as defined by the DSM-5 criteria. An interactive web response system (IWRS) or equivalent will be used to obtain an

identification (ID) number for each subject with documented consent. Although the screening period will continue up to administration of the first dose of investigational medicinal product (IMP), screening procedures should be initiated with a sufficient amount of time allotted in order to obtain laboratory results and electrocardiogram (ECG) results from the central reader prior to randomization. The sponsor reserves the right to utilize external quality oversight methods to ensure the validity of diagnosis, severity of illness, and other factors determining appropriateness of subject selection.

[figure not shown]
All subjects must agree to discontinue all prohibited medications during the screening period in order to meet the protocol-specified washout periods.

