- A standard 12-lead ECG will be performed after the subject has been supine and at rest for at least 5 minutes. See Table 3.4.3-1 for exclusions based on ECG results.

- Blood samples for clinical laboratory tests (hematology, coagulation parameters, and serum chemistry, including prolactin, HbA1c, and thyroid-stimulating hormone [TSH] with reflex to free thyroxine [T₄] if the result for TSH is abnormal, and lithium, valproate, and carbamazepine levels) should be drawn after a minimum 8-hour fast at screening. See Table 3.4.3-1 for exclusions based on outcome of screening clinical laboratory tests. Note: if lithium, valproate, or carbamazepine levels are outside of the listed exclusionary range, they may be reassessed prior to randomization.
- Samples will be obtained for blood alcohol testing. See Section 3.4.3 for details regarding subjects with a positive blood alcohol test.
- CCI [REDACTED]
- Urine will be collected from all potential subjects for urinalysis and urine screen(s) for drugs of abuse. See Section 3.4.3 for exclusions based on outcome of screening urinalysis and urine screen(s) for drugs of abuse.
- A urine pregnancy test will be performed for all women of childbearing potential (WOCBP). All positive results must be confirmed by a serum pregnancy test. Subjects with a positive serum pregnancy test result will be excluded from the trial.
- Adverse events will be recorded beginning with the completion of the consent process.
- Trial personnel will access the IWRS or equivalent to register the visit (initial visit only).

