9.1 Adverse Events

All adverse events will be coded by System Organ Class (SOC) and Preferred Term (PT) according to the Medical Dictionary for Regulatory Activities (MedDRA). AEs that are sex-specific, e.g., ovarian cancer, will have their incidence rates evaluated for the specific sex.

Treatment-emergent AEs (TEAEs) are defined as AEs with an onset date on or after the start of double-blind treatment period. In more detail, TEAEs are all adverse events which started after start of double blind IMP; or if the event was continuous from baseline and was worsening, serious, study drug related, or resulted in death, discontinuation, interruption or reduction of study therapy. Adverse events occurring up to 30 days after the last day of IMP will be included in the summary tables.

The incidence of the following events in the double-blind treatment period will be tabulated by treatment group and overall using the Safety Sample:

- a) TEAEs
- b) TEAEs by severity
- c) TEAEs potentially causally related to the IMP
- d) TEAEs with an outcome of death
- e) Serious TEAEs
- f) TEAEs leading to discontinuations of the IMP

The above summaries (b), (e) and (f) will also be prepared for TEAEs potentially causally related to the IMP.

In addition, incidence of TEAE during the double-blind treatment period of at least 5% in any treatment group other than placebo group, and also greater than placebo by SOC and PT will be provided.

Incidence of TEAEs by SOC and PT will be summarized for sex, race, age and region subgroups.

CCI

Unless otherwise specified, in general, analysis of safety data will be performed on observed case and for last visit.

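### Protocol 5.2 makes any change in AE severity a new AE and SAP 9.1 does not compare it with the pre-dose record, so an ongoing screening AE that eases after dosing can count as a TEAE

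*Protocol*

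**What the plan says.** **Collection starts before dosing.** Protocol 3.7.1.1 states: "Adverse events will be recorded beginning with the completion of the consent process". Protocol 5.2 agrees: "All AE collection is to begin after a subject has signed the ICF". The period from consent to first dose lasts up to 14 days, and Protocol 3.1 gives its aim: "The purpose of the screening period is to assess eligibility criteria and to washout prohibited concomitant medication". Protocol 4.1.1 expects adverse events in that period. It provides rescue medication for "treatment-emergent AEs (TEAEs) of anxiety, agitation, and insomnia will be allowed both during the washout period" as well as for the treatment phase.

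**A change makes a new AE.** Protocol 5.1 uses three grades, mild, moderate and severe: "Adverse events will be graded on a 3-point scale and reported as indicated on the ePlatform". Protocol 5.2 then sets the recording rule: "A reported AE that undergoes a change in severity, seriousness, or toxicity should be reported as a new AE on the ePlatform".

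**Treatment emergence goes by start date.** SAP 9.1 opens with: "Treatment-emergent AEs (TEAEs) are defined as AEs with an onset date on or after the start of double-blind treatment period". It then expands this: "TEAEs are all adverse events which started after start of double blind IMP; or if the event was continuous from baseline and was worsening". The list that follows the worsening condition adds events that were serious, were related to study drug, or led to death or to stopping, interrupting or reducing therapy. The definition therefore has two limbs joined by *or*. The first asks only when the AE started. The second sets conditions on an event already present at baseline.

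**The concern.** The second limb shows what the SAP wants: an AE carried over from screening should count only if something adverse happened to it, such as worsening. The recording rule in Protocol 5.2 works against this. Its word for change has no direction, so a fall from severe to moderate opens a new AE just as a rise does. If that new AE starts after the first dose, it meets the first limb and the worsening test is never reached. An improvement is then tabulated as an emergent event.

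There is a second, smaller problem in the same sentence. Being serious is listed without a time limit, so an SAE that began in screening and is unchanged after dosing satisfies the second limb as written.

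Safety and tolerability is the trial's secondary objective. One definition feeds the overall TEAE table, the tables by severity and for serious events, the table of events at 5% or more, and the subgroup tables.

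**Working it through.** The plan gives no figure to reproduce here, so the check is mainly a reading of two rules against each other.

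**1. One subject followed through the rules.** Insomnia is recorded as a severe AE during washout and is still present at first dose. On Day 5 it is mild.

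| Step | Rule | Result |
|---|---|---|
| Severe to mild | Protocol 5.2 | New AE record, because severity changed |
| Onset of new record | Not stated; taken as the date of change | Day 5 |
| First limb | SAP 9.1 | Met: started after IMP |
| Worsening test | SAP 9.1, second limb | Not reached |

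The same insomnia left at severe gives no new record and, with no other listed condition met, is not a TEAE. The subject who improved is counted and the subject who did not is left out.

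**2. What is left for the second limb.** If Protocol 5.2 is followed, a rise in grade is also a new record, so no single record worsens in grade. The worsening test can work only if records of the same event are linked, and no visible text says how. The same holds for seriousness. An event that becomes serious after dosing is a new record and already meets the first limb. Read record by record, the word serious in the second limb therefore adds only events that were serious before dosing.

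**3. How narrow the path is.** All of these must hold:
- The symptom was recorded as an AE. Protocol 5.2 admits exacerbation of the disease itself only with unusual or severe features.
- It was ongoing at first dose and moderate or severe, since a mild AE has no lower grade.
- It dropped a grade without resolving. Resolution gives an end date, not a new AE.
- The new record carries the date of change as its onset.

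**4. Scale, under assumptions only.** The documents give no screening-AE or easing rates. Let *g* be the genuine TEAE rate for one preferred term, and *w* the probability, taken as independent of *g*, that a subject has an eased washout record of that term. The tabulated rate is p = 1 − (1 − g)(1 − w). With the planned 160 per arm, 5% is 0.05 × 160 = 8 subjects. The chance that a term reaches 8 in the active arm is the binomial tail P(X ≥ 8; 160, p). With g = 3% assumed:

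| w | p | P(X ≥ 8) |
|---|---|---|
| 0 | 3.00% | 11% |
| 1% | 3.97% | 30% |
| 2% | 4.94% | 54% |

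The table's further condition, incidence greater than placebo, is not modelled.

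**5. Effect on the comparison, again with assumed rates.**
- Equal contamination dilutes the ratio. Genuine 10% versus 5% (ratio 2.00) with w = 5% in each arm becomes 14.5% versus 9.75% (ratio 1.49).
- Unequal contamination creates a difference. Genuine 4% in both arms with w = 6% on active and 3% on placebo gives 1 − 0.96 × 0.94 = 9.76% versus 1 − 0.96 × 0.97 = 6.88% (ratio 1.42). With the two values of w exchanged, the ratio is 6.88/9.76 = 0.70.

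**The case against.** The best defence reads SAP 9.1 by event and not by record. Insomnia that eases is still the same insomnia, continuous from baseline, so a programmer could apply the worsening test to it. That reading gives the second limb something to do and is probably the intent. However, the opening definition goes by the onset date of the AE, Protocol 5.2 calls the changed event a new AE, and nothing visible says which records form one event. Part of SAP 9.1 is blacked out and SAP section 10.2 is not in the text available, so a linking convention there cannot be ruled out. This limits confidence in the consequence but does not remove the conflict between the visible rules.

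The path is also narrow, and that stands. Sleep, irritability and motor activity are YMRS items, so much washout disturbance may be judged part of the index mania and never entered as an AE. Protocol 4.1.1 nevertheless treats anxiety, agitation and insomnia in washout as AEs, so the number cannot be taken as zero.

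On seriousness, most of the neighbouring conditions describe things that happen after dosing, so *became serious* is a plausible intended meaning. Subjects with an SAE in screening who are still randomized should be rare under the medical exclusions. The point is a wording correction, though with few serious events one case can matter.

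A reader might infer that an effective drug would push these records onto the active arm. The documents do not support that. An effective drug also brings more complete resolution, which creates no new record, and partial easing could be commoner on placebo. A reader might also estimate how many subjects have any eased AE and compare that with the 8 needed for the 5% table. That comparison fails: the table is by system organ class and preferred term and also requires an excess over placebo. For overall incidence, a subject who has a genuine TEAE as well adds nothing.

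**Conclusion.** The point holds as a defect in how the two rules combine. Applied literally, they count as treatment-emergent an AE recorded before dosing that is still ongoing and drops a grade without resolving after the first dose, although the second limb of SAP 9.1 would count a continuing event only for worsening or another listed reason. The literal wording also brings an unchanged pre-dose SAE into the Serious TEAE table.

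The conclusion about eased AEs rests on one inference, that the new record starts on the date of change, and on there being no linking rule in text that cannot be seen. The effect is over-inclusion, which can dilute or distort the comparison of arms. Its size and direction are not known from the documents, and the percentages in the working are illustrations only. The TEAE tables are descriptive, and the primary and key secondary analyses are unaffected. It is still worth correcting, because these tables are a main output for the secondary objective.

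**What to change.** Change SAP 9.1 and leave Protocol 5.2 as it is, so that the full severity history is kept.

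1. **Link** a post-dose record to a pre-dose record only when it is the same event continuing without a gap: same preferred term, with the end date of the earlier record meeting the start date of the new one. Follow the chain if the grade changes more than once.
2. **Count** a linked record as treatment-emergent only if its severity exceeds the worst pre-dose severity, if it became serious after the first dose, or if it met another of the second limb's listed conditions after the first dose.
3. **Reword** the unqualified condition of being serious to having become serious after the first dose.
4. **Keep recurrences.** An event that resolved before dosing and returned afterwards counts as a new TEAE. Linking by preferred term alone would hide such events.
5. **State** that a record opened for a change in severity takes the date of change as its onset.

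The cost is a few sentences in the SAP, a small programming step that also handles data already entered, and slightly lower TEAE counts. One consequence to accept openly is that an event that eases and then partly returns, without exceeding its worst pre-dose grade, is not counted unless another listed condition is met. No visit, dose, endpoint or efficacy analysis changes.
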